syndrome, somatostatin analogue therapy is not permitted after embolization or chemoembolization.

VII. EXPECTED TOXICITIES AND DOSE ADJUSTMENT

1. Dose adjustment after the first embolization or chemoembolization

No dose adjustment of doxorubicin or streptozotocin is planned for chemoembolization sessions. There are no plans to adjust the dose of lipiodol for embolization sessions.

Embolization or chemoembolization will only be performed if hematological, renal and hepatic functions are satisfactory i.e. if:

- PNN $\geq 1.5 \times 10^9$ /L,
- Platelets $\geq 75 \times 10^9$ /L
- Hemoglobin ≥ 10 g/dL
- INR $< 1.3N$ or < 3 on anticoagulants or PT ≥ 50
- Creatinine level $\leq 1.5N$
- Total bilirubin $< 1.5N$
- ASAT, ALAT $\leq 5N$
- PAL $< 5N$

In case of grade 3 or 4 non-hematological toxicity attributable to the first embolization or chemoembolization session, no further embolization or chemoembolization is performed. Only everolimus will be continued for a maximum of 24 months.

2. Everolimus dose adjustment

All toxicity will be assessed according to the NCI-CT v4.0 scale (Appendix 4).

The rules for everolimus dose adjustment in case of observed hematological and non-hematological toxicities are defined in Tables 1.1, 1.2.

All interruptions or changes to the study drug must be recorded

Monitoring of suspected everolimus toxicity

Patients whose treatment is temporarily or permanently discontinued due to an adverse event or laboratory abnormality suspected to be related to everolimus should be monitored at least weekly until the adverse event resolves or returns to grade 1. If the patient's treatment is to be delayed for more than 21 days from the day of the next scheduled dose, the patient should be excluded from the study.

Table 1.0 Guidelines for Everolimus Dose Level Changes

Dose level	Dose and frequency of administration
0 (initial dose)	10 mg per day
-1	5 mg per day
-2	5 mg every 2 days

a. **Dose adjustment for non-hematologic and hematologic toxicities**

Table 1-1 Dose adjustment criteria for everolimus toxicity and reinstatement of everolimus therapy

NON-HEMATOLOGICAL AND NON-HEPATIC Toxicity (NCI-CTC V4.0)	Actions

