Grade 2 (except pneumonia - see Table 1-4)	If toxicity is tolerable to the patient, maintain the same dose. In case of intolerable toxicity for the patient, discontinue everolimus until recovery to grade ≤ 1 . Then reintroduce everolimus at the same dose. If an event returns to grade 2, discontinue everolimus until recovery to grade ≤ 1 . Then reintroduce everolimus at the lower dose level.
Grade 3 (except hyperlipidemia*) (except pneumonia - see Table 1-4)	Interrupt everolimus until recovery to grade ≤ 1 . Then reintroduce everolimus at the lower dose level. For pneumonia, consider short-term steroid therapy.
Grade 4	Stopping everolimus
Any non-hematologic toxicity requiring interruption for a period ≥ 3 weeks	Stopping everolimus

*Grade 3 hyperlipidemia (hypercholesterolemia and/or hypertriglyceridemia) should be managed with medical treatments.

Table 1-2

HEMATOLOGICAL Toxicity (NCI-CTC V4.0)	Grade	Actions
Thrombocytopenia	Grade 2 (platelets $< 75, \geq 50 \times 10^9 /l$)	Interrupt everolimus until recovery to grade ≤ 1 ($\geq 75 \times 10^9 /l$). Then reintroduce everolimus at the initial dose. If thrombocytopenia returns to grade 2, discontinue everolimus until recovery to grade ≤ 1 . Then reintroduce everolimus at the lower dose level.
	Grade 3 (platelets $< 50, \geq 25 \times 10^9 /l$)	Interrupt everolimus until recovery to grade ≤ 1 (platelets $\geq 75 \times 10^9 /l$). Then resume everolimus at a lower dose level.

		If thrombocytopenia recurs at grade 2, discontinue everolimus.
	Grade 4 (platelets < 25×10^9 /L)	Stopping everolimus
Neutropenia	Grade 3 (neutrophils < 1, $\geq 0.5 \times 10^9$ /L)	Interrupt everolimus until recovery to grade ≤ 1 (neutrophils $\geq 1.5 \times 10^9$ /L). Then resume everolimus at the initial dose. If PNN returns to grade 3, withhold everolimus until PNN is $\geq 1.5 \times 10^9$ /L. Then resume everolimus at the lower dose level. Discontinue study treatment if a third episode of Grade 3 neutropenia occurs
	Grade 4 (neutrophils < 0.5×10^9 /L)	Interrupt everolimus until recovery to grade ≤ 1 (neutrophils $\geq 1.5 \times 10^9$ /L). Then resume everolimus at the lower dose level. If Grade 3 or 4 neutropenia occurs despite this dose reduction, discontinue everolimus

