HBsAg	+ or -.	+	-	-	-
HBsAb	+ or -.	+ or -.	+ and without prior HBV vaccination	+ or -.	- or + with previous HBV vaccination
HBsAb	+ or -.	+ or -.	+ or -.	+	-
Recommendation	Prophylaxis should be initiated 1-2 weeks prior to the first dose of study drug Monitor HBV DNA approximately every 6 weeks		No prophylaxis Monitor HBV DNA approximately every 3 weeks		No specific action

Antiviral prophylaxis should be continued for at least 4 weeks after the last dose of study drug.

For the definition of hepatitis B reactivation and guidelines for its management, refer to Table 2-2.

Table 2-2: Hepatitis B Management Guidelines

HBV reactivation (with or without clinical signs and symptoms)*.	
For patients with initial findings: HBV DNA positive OR HBsAg positive	Treat: Start a second antiviral AND Discontinue study drug until resolution: \leq baseline levels of HBV DNA In case of resolution within \leq 28 days the study drug should be restarted at a lower dose, if available. If the patient is already receiving the lowest dose of study drug per protocol, the patient should restart the study drug at the same dose after resolution. Both antiviral therapies should be continued for at least 4 weeks after the last dose of study drug is administered.
Reactivation is defined as: [1-log increase in HBV DNA from baseline HBV	

DNA OR new onset of measurable HBV DNA]	If resolution occurs within >28 days patients should discontinue study drug but continue both antiviral treatments for at least 4 weeks after the last dose of study drug.
For patients with initial results: HBV DNA and HBsAg negative AND [HBsAb positive (with no prior history of HBV vaccination), OR HBcAb positive] ----- reactivation is defined as follows: New appearance of measurable HBV DNA	Treat: Start antiviral medication AND Discontinue study drug until resolution: ≤ baseline levels of HBV DNA In case of resolution within ≤ 28 days the study drug should be restarted at a lower dose, if available. If the patient is already receiving the lowest dose of study drug per protocol, the patient should restart the study drug at the same dose after resolution. Antiviral therapy should be continued for at least 4 weeks after the last dose of study drug is administered. In case of resolution within > 28 days patients should discontinue study drug, but continue antiviral therapy for at least 4 weeks after the last dose of study drug.

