* All hepatitis B reactivations should be recorded as a Grade 3 adverse event (CTCAE v 4.0 Other Adverse Events Associated with Metabolic or Biological Abnormalities: Viral Reactivation), unless the investigator considers them life-threatening in which case they should be recorded as a Grade 4 adverse event (CTCAE v 4.0 Other Adverse Events Associated with Metabolic or Biological Abnormalities: Viral Reactivation). The date of viral reactivation is the date on which **both** the DNA and ALAT criteria are met (e.g., for a patient with HBV DNA positive on 01-01-10 and an ALAT level $\geq 5 \times$ ULN on 01-04-10, the date of viral reactivation is 01-04-10).

• Hepatitis C Outbreak Surveillance

The following two categories of patients should be monitored every 6 weeks for HCV reactivation:

- Patients with detectable HCV RNA by PCR analysis in basal state.
- Patients with a known history of hepatitis C virus (HCV) infection, despite a negative baseline viral load test (including those who have been treated and considered "cured")

For the definition of hepatitis C reactivation and guidelines for its management, see Table 2-3 Guidelines for the Management of Hepatitis C.

Table 2-3: Guidelines for the Management of Hepatitis C

HCV outbreak	
For patients with baseline results: detectable HCV RNA, an HCV outbreak is defined as follows:	Discontinue study drug but continue monitoring as part of the study.

Increase in HCV RNA by $2 \log_{10}$ IU/ml AND ALT elevation: $5 \times$ ULN or $3 \times$ baseline, whichever is higher
	

For patients with baseline results: Known history of hepatitis C without detectable HCV RNA, an HCV outbreak is defined as: New appearance of detectable HCV RNA AND ALT elevation: $5 \times$ ULN or $3 \times$ baseline, whichever is higher
	
Discontinue study drug but continue monitoring as part of the study. .

* All hepatitis C outbreaks should be recorded as a Grade 3 event (CTCAE v 4.0 Other Adverse Events Associated with Metabolic or Biological Abnormalities: Viral Outbreak), unless the investigator considers them life-threatening, in which case they should be recorded as a Grade 4 event (CTCAE v 4.0 Other Adverse Events Associated with Metabolic or Biological Abnormalities: Viral Outbreak)

VIII. PATIENT MONITORING DURING TREATMENT AND AFTER WITHDRAWAL OF TREATMENT

1. Monitoring during treatment

Within 7 days prior to each embolization or chemoembolization session

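### The protocol does not say whether Table 1-1 and the 21-day limit apply to hepatitis B reactivation or whether Table 2-2 overrides them, and they can lead to different actions on everolimus

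*Protocol*

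**What the plan says.** Four places in Protocol section VII.2 bear on a patient whose hepatitis B reactivates on everolimus.

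- **Table 2-2 (VII.2.f).** Its scope is "HBV reactivation (with or without clinical signs and symptoms"), so it covers every reactivation. Everolimus is held until HBV DNA is at or below its baseline level. If this happens within 28 days, "the study drug should be restarted at a lower dose, if available", and a patient already on the lowest level resumes at that level. For slower resolution: "In case of resolution within > 28 days patients should discontinue study drug".
- **Footnote to Table 2-2.** Every reactivation is recorded as grade 3, "unless the investigator considers them life-threatening in which case they should be recorded as a Grade 4 adverse event". The recording category is "Other Adverse Events Associated with Metabolic or Biological Abnormalities: Viral Reactivation".
- **Table 1-1 (VII.2.a).** The column header reads "NON-HEMATOLOGICAL AND NON-HEPATIC Toxicity (NCI-CTC V4.0"). The grade 4 action is "Stopping everolimus", and the same action applies to any non-hematologic toxicity that needs an interruption of 3 weeks or more.
- **VII.2, opening text.** "The rules for everolimus dose adjustment in case of observed hematological and non-hematological toxicities are defined in Tables 1.1, 1.2". The paragraph on monitoring suspected everolimus toxicity adds that a patient whose treatment is delayed by more than 21 days is to be excluded from the study.

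No sentence ranks these rules against one another for viral reactivation.

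**The concern.** The footnote separates grade 3 from grade 4 reactivations, but the table it belongs to makes no use of the distinction. A site that looks up the recorded grade in Table 1-1 finds a permanent stop. A site that looks up the event in Table 2-2 finds a restart that depends only on HBV DNA and elapsed time. Two sites acting in good faith could therefore handle the same life-threatening event differently. The same can happen to a less severe reactivation that takes three to four weeks to resolve.

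The main stake is an ambiguous safety instruction. A smaller one is reporting: the SAP describes treatment duration, compliance and the reasons for permanent cessation, and each would partly reflect which rule the site followed.

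**Working it through.** No sample-size or event figure is involved, so the check is a comparison of the rules, with one piece of day arithmetic.

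**Step 1. Is the event inside Table 1-1?** The documents point both ways.

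- *Inside:* the footnote's recording category is metabolic or biological, not hepatic. VII.2.b mentions hepatitis B reactivation among viral infections. Table 2-2 defines reactivation by HBV DNA alone. The opening sentence of VII.2 presents Tables 1.1 and 1.2 as the rules for hematological and non-hematological toxicities, with no hepatic carve-out.
- *Outside:* the column header of Table 1-1 excludes hepatic toxicity. Section VII.2.f is about hepatitis and refers the reader to Table 2-2 for its management. The footnote's rule for dating a reactivation uses a transaminase criterion as well as HBV DNA.

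The question stays open on the text.

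**Step 2. What follows for a grade 4 reactivation under each reading?**

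| Time to HBV DNA resolution | Table 2-2 | Table 1-1 grade 4 row, if it applies |
|---|---|---|
| 28 days or less | restart | stop |
| more than 28 days | discontinue | stop |

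The outcomes differ only in the first row. Beyond 28 days the two tables agree.

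**Step 3. The time limits, at either grade.** Take 3 weeks = 3 × 7 = 21 days. Assume that the interruption lasts as long as resolution takes and that all clocks start together.

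| Length of interruption | Table 2-2 | Table 1-1, 3-week row | VII.2, 21-day paragraph |
|---|---|---|---|
| under 21 days | restart | no stop | no exclusion |
| exactly 21 days | restart | stop | no exclusion |
| 22 to 28 days | restart | stop | exclude |
| over 28 days | discontinue | stop | exclude |

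Table 2-2 conflicts with the 3-week row on days 21 to 28 (28 − 21 + 1 = 8 days) and with the 21-day paragraph on days 22 to 28 (28 − 22 + 1 = 7 days). The real clocks may differ by a day or so: the 21-day paragraph counts from the next scheduled dose, and Table 2-2 does not say when its 28 days begin.

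**Step 4. How far does this second conflict depend on the header?** The 3-week row sits in Table 1-1 but is itself worded for any non-hematologic toxicity. The 21-day paragraph is outside every table and carries no hepatic exception. It concerns events suspected to be related to everolimus, and VII.2.b describes hepatitis B reactivation in patients on the drug. This conflict therefore survives even if Table 1-1 is set aside.

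**The case against.** The strongest reply is that a specific rule governs over a general one. VII.2.f is a dedicated section, it refers the reader explicitly to Table 2-2, and Table 1-1 announces that it is not for hepatic toxicity. The footnote says how the event is recorded, not which dose table applies. On that reading the grade 4 rows never meet. This stands as a reasonable reading, so a reader who infers that the two tables plainly give opposite instructions for the same event goes further than the text allows. It remains a reading, however. The protocol states no precedence here, whereas for pneumonia Table 1-1 sends the reader to Table 1-4.

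Three other inferences are tempting and should be resisted.

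- *That Table 2-2 always restarts the drug, so the contrast is none restarted against all restarted.* Restart is limited to resolution within 28 days. Section IX also lets treatment end on the investigator's decision, for major toxicity or for a serious event. No such percentages follow from the documents.
- *That Table 1-1 must cover viral reactivation because it lists exceptions for pneumonia and hyperlipidemia but none for reactivation.* Those exceptions stand in the grade 2 and grade 3 rows. The grade 4 row has none for anything, so the omission says nothing about grade 4.
- *That Table 2-2 is the unsafe rule.* The documents do not settle which instruction is clinically right, and this point takes no view.

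Section IX softens the problem, because an investigator can stop treatment whatever Table 2-2 says. It does not tell a site which rule is the default. Nor does the specific-over-general argument clearly remove the 21-day paragraph, which is written for all suspected everolimus toxicity.

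**Conclusion.** The point holds as an unresolved overlap with two parts. First, for a reactivation recorded as grade 4 and resolving within 28 days, Table 1-1 (if it applies despite its header) and Table 2-2 lead to different actions. Second, for a reactivation of either grade resolving between about day 21 and day 28, the restart in Table 2-2 conflicts with the 21-day exclusion and the 3-week stop. The second part is the firmer, because the 21-day paragraph does not depend on the scope of Table 1-1.

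The size is small in numbers. Such events are expected to be few, and the documents give no frequency. The primary endpoint is not directly affected: death or liver progression counts as failure whether or not everolimus continues, and discontinued patients stay in the intention-to-treat analysis. The consequence is for consistent patient management and for the exposure and discontinuation tables. The conclusion rests on the absence of any precedence statement in the available text and, for the day counts, on the common starting point assumed above.

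**What to change.** Reconcile the opening text of VII.2, Table 1-1, Table 2-2 and its footnote by stating:

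1. whether Table 1-1 applies to hepatitis B reactivation;
2. whether the 21-day exclusion and the 3-week stop apply to it, and from which day each limit and the 28-day window are counted;
3. which rule prevails where they differ;
4. whether the footnote's grade 3/grade 4 distinction changes the action in Table 2-2 or serves recording only.

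The clinical team decides the content of each answer. A cross-reference between Tables 1-1 and 2-2, like the one already used for pneumonia, would carry the decision to sites. The cost is protocol wording: no new assessments, no extra patients and no change to the primary analysis.

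### The Table 2-2 footnote dates hepatitis B reactivation by HBV DNA and ALAT together, although Table 2-2 defines reactivation by HBV DNA alone (minor)

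*Protocol*

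**What the plan says.** Protocol section VII.2.f names one source for the definition: "For the definition of hepatitis B reactivation and guidelines for its management, refer to Table 2-2". The heading of that table reads "HBV reactivation (with or without clinical signs and symptoms", and its asterisk leads to the footnote.

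Table 2-2 gives two definitions.
- **Baseline HBV DNA or HBsAg positive:** the criterion starts "1-log increase in HBV DNA from baseline HBV" and has new measurable DNA as the alternative.
- **Baseline DNA and HBsAg negative, with relevant antibodies:** "New appearance of measurable HBV DNA".

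In both groups a reactivation calls for antiviral treatment (a second antiviral in the first group) and for stopping the study drug until HBV DNA is back to its baseline level.

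The footnote makes two statements. On grading: "All hepatitis B reactivations should be recorded as a Grade 3 adverse event", or Grade 4 if life-threatening. On dating: "The date of viral reactivation is the date on which", then the emphasised word both, then "the DNA and ALAT criteria are met". Its example has a positive DNA result on 01-01-10 and ALAT of at least 5 x ULN on 01-04-10, and takes the second date.

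Table 2-3, for hepatitis C, does pair the viral marker with ALT, for instance "New appearance of detectable HCV RNA AND ALT elevation".

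**The concern.** The dating rule calls on a criterion that the definition does not contain. An event can therefore be a reactivation under the table and have no date under the table's own footnote. If ALAT rises later, the recorded onset falls after the antiviral start and the everolimus interruption that the event had already required.

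Every hepatitis B reactivation is at least Grade 3, and Protocol XII.3 (Main analyses) plans a Kaplan-Meier estimate of time to onset of grade 3/4/5 toxicity. A missing or late date would enter that estimate. If the analysis takes each patient's first such event, which the protocol does not say, the date matters only when the reactivation comes first.

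**Working it through.** There is no planned figure to reproduce. The check sets the two rules side by side and then bounds the delay.

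**Definitions**

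| Source | Viral criterion | ALAT/ALT criterion |
|---|---|---|
| Table 2-2, DNA or HBsAg positive | 1-log DNA rise or new measurable DNA | none |
| Table 2-2, DNA and HBsAg negative | new measurable DNA | none |
| Table 2-2 footnote (date only) | DNA | required; no general threshold, 5 x ULN in the example |
| Table 2-3, RNA detectable at baseline | 2-log RNA rise | 5 x ULN or 3 x baseline, whichever is higher |
| Table 2-3, history without detectable RNA | new detectable RNA | same |

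So 0 of 2 hepatitis B definitions contain ALAT, against 2 of 2 hepatitis C definitions. Text lost in PDF reading is an unlikely cause: both hepatitis B definitions read as complete, and the ALT terms of the similarly laid-out Table 2-3 came through.

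**The footnote's own example**

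If the DNA result of 01-01-10 meets the table's criterion, Table 2-2 gives 01-01-10 and the footnote gives 01-04-10. Read day-month-year, the gap is 31 + 28 + 31 = 90 days; read month-day-year, it is 3 days. If ALAT never reaches the threshold, the footnote gives no date.

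**Delay when ALAT rises later**

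Inputs:
- Scheduled ALAT testing every 3 months, +/- 1 week (Protocol VIII.1).
- HBV DNA about every 3 or 6 weeks, depending on the serology (Table 2-1).
- 1 month = 30.4375 days (SAP 7.1.3).
- At least weekly monitoring after an interruption for an event suspected to be related to everolimus (Protocol VII.2 and VIII.1). No tests are listed for it.

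Scheduled ALAT interval: 3 x 30.4375 = 91.3 days. Delay = 91.3 minus the day of the first DNA draw that meets the criterion, counted from the last 3-monthly visit. This assumes that ALAT is raised at the next scheduled test; a later rise lengthens the delay.

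| DNA draw (day after visit) | 3-weekly group | 6-weekly group |
|---|---|---|
| 21 | 91.3 - 21 = 70.3 | no draw |
| 42 | 91.3 - 42 = 49.3 | 49.3 |
| 63 | 91.3 - 63 = 28.3 | no draw |
| 84 | 91.3 - 84 = 7.3 | 7.3 |

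The visit window moves each value by up to 7 days either way; for example, 70.3 becomes 63.3 to 77.3. If the weekly monitoring includes ALAT, the delay is about 7 days in either group.

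**The case against.** The mismatch is hard to dispute, but its consequence and its repair can be.

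**The date has little use.** SAP 7.6.4 describes toxicity by maximum grade and has no time-to-onset analysis. All adverse events go into the observation booklet (Protocol XI), so having no date under the footnote does not show that the event would have no onset date at all. Both points stand and hold the finding at minor.

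**Long delays need an unlikely course.** A reader might take 49 or 70 days as the size of the problem. The documents do not support that. Those values require the DNA criterion to be met early after a 3-monthly visit and no ALAT test before the next one. Weekly monitoring after an interruption may well include ALAT. Protocol XII.2 mentions monthly toxicity visits, without listing tests, and ALT is also measured before each embolization session. The 70-day value applies only to the 3-weekly group, who are HBsAg negative. Protocol III and SAP 7.2.4 foresee the further HBV tests only when HBsAg is positive, so study testing might not identify that group, although the examination schedule lists all four tests. This stands.

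**The footnote may be what was intended.** Its emphasis and worked example look deliberate, and the bracketed alternative in the first definition could be what remains of a longer rule. The documents do not settle the intention. However, the definition, the resolution rule and the dedicated HBV monitoring all rest on DNA, and the second definition gives no hint of a missing term.

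**Readings that go too far.** A reader might infer that the footnote delays antiviral treatment or the stopping of everolimus. It does not: those actions follow from the DNA-based definition, and the footnote sets only a date. Nor does it shift the SAE clock, which runs from discovery (Protocol XI), the maximum-grade tables or the primary endpoint. Table 2-2 makes restarting the drug depend on resolution within 28 days without saying when the count starts. Nothing ties that count to the footnote's date, so no effect on restarting can be claimed.

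**Conclusion.** Wrong as written; minor. The footnote applies an ALAT condition that exists nowhere in the hepatitis B definition. It leaves a DNA-only reactivation undated under its rule and dates one with a later ALAT rise after the action it triggered.

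The reach is narrow: patients with positive HBV markers among the planned 72, a number that the documents do not give, and one Kaplan-Meier analysis that the protocol names and the SAP does not take up. The delay is not a fixed quantity. It is about 7 days if weekly monitoring includes ALAT, and about 7 to 70 days if ALAT is tested only at 3-monthly visits, depending on which DNA draw meets the criterion.

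The mismatch itself rests on no assumption. The delay figures rest on the testing schedules above and on ALAT being raised at the next test. The effect on the Kaplan-Meier estimate also depends on whether the observation booklet collects a separate onset date, which cannot be seen from the documents.

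**What to change.** Replace the dating sentence in the Table 2-2 footnote with: the date of viral reactivation is the date on which the HBV DNA criterion of Table 2-2 is first met. Delete the ALAT example.

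If the sponsor did intend an ALAT condition, record the ALAT rise as a separate item, such as a hepatitis flare date, and leave the DNA-based treatment trigger and onset date unchanged. Adding ALAT to the definition instead would narrow a safety trigger and could call for more ALAT testing.

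The main change is an edit to one footnote, with no added visit, procedure or test. The separate flare date, if wanted, would add one item to record.
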